6.3.3 Recommendations for Modifications of Camrelizumab

No dose adjustment is allowed, only suspension of administration is allowed. The withdrawal criteria can be referred to the NCCN Guidelines for immune-related Adverse Reactions

7. Adverse Event

7.1 Definition

An adverse event (AE) is an adverse medical event that occurs after a clinical trial subject receives a drug, but is not necessarily causally related to the treatment. An AE can be any adverse and undesired symptom, sign, laboratory abnormality, or disease, including at least the following:

- 1) The pre-existing medical condition/disease (prior to entry into the clinical trial) is only recorded as an adverse event if it worsens (including worsening of symptoms, signs, and abnormalities in laboratory tests) after initiation of the investigational drug;
- 2) Any newly occurring AE: any newly occurring adverse medical condition (including symptoms, signs, and newly diagnosed diseases);
- 3) Abnormal clinically significant laboratory test results.

Invasive (e.g., surgery), non-invasive procedures that are diagnostic or therapeutic should not be reported as AE, but should be reported when the disease conditions that led to the procedure meet the definition of AE, such as acute appendicitis that developed during the reporting period of AE should be reported as AE, and appendectomy performed as a result should be recorded as the treatment for that AE.

The investigator should record in detail any AE that occurred in the subject, including the name of the AE, time of occurrence and end, severity (graded according to NCI CTCAE <5.0>), correlation between the AE and the trial drug, duration, measures taken on the trial drug due to the AE, outcome of the AE, and whether it was a serious adverse event.

7.2 Recording and Management

Researchers should observe any adverse events that occur during the study, and require subjects to truthfully report changes in their condition after receiving treatment and avoid leading questions. Watch for adverse events or unanticipated clinical manifestations and adverse events (including symptoms, signs, and laboratory tests) while observing efficacy. Adverse events, whether related to the investigational drug or not, should be recorded in detail in the CRF, and the combination of drugs should be recorded in detail to analyze the relevance of adverse events to clinical procedures and drugs, and the record should be signed and dated.

Medical treatment of subjects: When adverse events are found, the investigator may take necessary treatment measures according to the condition, such as surgical intervention, adjustment of chemotherapy dose, temporary interruption of treatment, etc., and decide whether to terminate the trial. In the event of serious adverse events, necessary treatment measures should be taken immediately to protect the safety of subjects.

7.3 AE Severity Grading

Table 5 AE Severity Grading

Severity (Toxicity Grade)	Description
Grade 1	Mild; asymptomatic or mild symptoms; clinical or diagnostic observations only; intervention not indicated
Grade 2	Moderate; minimal, local or noninvasive intervention indicated; limiting ageappropriate instrumental activities of daily living (ADL)
Grade 3	Severe or medically significant but not immediately life-threatening; hospitalization or prolongation of hospitalization indicated; disabling; limiting self-care ADL
Grade 4	Life-threatening consequences; urgent intervention indicated
Grade 5	Death related to AE

7.4 The Relationship Between AEs and Experimental Drugs

The investigator shall conduct a comprehensive evaluation to determine whether the investigational drug has a reasonable probability of causing or contributing to AE, including whether there is a reasonable time sequence between the occurrence of AE and the administration of the investigational drug, the characteristics of the investigational drug, the toxicological and pharmacological effects of the investigational drug, the use of combined drugs, the subject's underlying disease, medical history, and other factors. Family history and deactivation and reactivation responses. The possible association between adverse events and the investigational drug was evaluated according to a five-level classification of "definitely relevant, probably relevant,

probably irrelevant, definitely irrelevant, and undetermined".

7.5 SAE Reporting

7.5.1 SAE Definition

SAE is an adverse event that occurs during the study that meets one or more of the following criteria: events leading to death;

life-threatening (the term "life-threatening" means that the subject is at risk of death at the time of the event/reaction; It is not assumed that an increase in illness may lead to death);

Events requiring hospitalization or prolonged hospitalization;

events resulting in permanent or serious disability/loss of function;

congenital abnormalities or birth defects;

Other medically important events.

7.5.2 SAE Reporting

In the event of an SAE, whether first report or follow-up report, the investigator must immediately complete, sign and date the Serious Adverse Event Report Form and report it to the appropriate authorities within 24 hours of the investigator becoming aware of it. If SAE occurs after initiation of study drug use, it should also be reported to Hengrui Drug Safety Department ([contact]).

All SAEs should record in detail the symptoms, severity (refer to NCI-CTCAE 5.0), correlation with each investigational drug, occurrence time, treatment time, measures taken by SAE for each investigational drug, follow-up time and method, and outcome. If the investigator considers an SAE unrelated to the investigational drug, but potentially related to study conditions (such as discontinuation of the original treatment, or comorbidities during the trial), this relationship should be detailed in the narrative section of the SAE report form. If the intensity of an ongoing SAE or its relationship to the investigational drug changes, a follow-up report should be submitted immediately. If an investigator believes that a previously reported SAE contains false positives, corrections, retractions, or downgrades may be made in the follow-up report and reported in accordance with SAE reporting procedures.

Any serious adverse event that occurs during the study, regardless of whether it is related to the study, should be dealt with promptly. The researcher should promptly study the serious adverse event and take necessary measures to ensure the safety and rights of the subjects. Researchers must complete a Serious Adverse Event Reporting Form, which should record in the original data when, how, and to whom the serious adverse event was reported.

Investigators must report all AEs, SAEs, and other safety events that occur after informed consent is signed, but before enrollment, if they result in exclusion from the study or are the result of protocol-mandated interventions (including, but not limited to, washout or discontinuation of usual treatment, diet, or procedures).

7.6 Pregnancy

If a female subject becomes pregnant during the study, the subject shall immediately terminate the use of the experimental drug and be discharged from the group; if a male subject's partner becomes pregnant during the clinical study, the subject shall continue the clinical study.

8 End of Treatment

A patient may be discontinued from study treatment at any time if the patient, the investigator, feels that it is not in the patient's best interest to continue on study. If a patient's study treatment must be discontinued, this will not result in automatic withdrawal of the patient from the study.

The following is a list of possible reasons for early discontinuation of study treatment:

Disease progression (patients should be highly encouraged to stay on study treatment until there is confirmed radiographic progression)

Any episode of seizure

Any other adverse event that cannot be adequately managed with dose modifications, including dose interruption for ≥ 28 days may require study drug discontinuation, which must be discussed with the Sponsor.

Protocol violation requiring discontinuation of study treatment

Patient is not compliant with study procedures

Lost to follow-up

Patient withdrawal of consent

9 Protocol Violations

A protocol violation occurs when the patient or Investigator fails to adhere to significant protocol requirements affecting the inclusion, exclusion, patient safety and primary endpoint criteria. Protocol violations for this study include, but are not limited to, the following:

- Failure to meet inclusion/exclusion criteria [no waivers will be granted to meet the eligibility criteria]
- Use of a prohibited concomitant medication
- Dose modifications that are not within the protocol specifications
- Any other deviation that presents significant risk or safety concerns to the patient

Failure to comply with Good Clinical Practice (GCP) guidelines will also result in a protocol violation. The Sponsor, in consultation with the Investigator, will determine if a protocol violation should result in withdrawal of a patient.

10 Statistic Method

10.1 Analysis Set

Full Analysis Set (FAS) : Patients who met the enrollment criteria and were treated with the study protocol.

Per Protocol Set (PPS) : This analysis set is defined as subjects with no significant protocol deviations during the study or no protocol deviations that have a significant impact on the study results.

Safety Set (SS) : Participants enrolled and receiving at least one cycle of treatment with at least one safety evaluation record constitute the safety set of the study.

The efficacy evaluation of this study will be based on FAS and PPS, in which FAS is the main analysis set. Safety analysis will be based on SS.

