2.1 Primary Endpoint

Tumor regression rate of MSS/pMMR patients (Pathological response, percentage of TRG2-4 to all MSS patients, Dworak criteria)

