3. ECOG 0-1
4. Surgical treatment is planned after completion of neoadjuvant therapy
5. Patients can swallow pills normally
6. Expected overall survival \geq 12 months
7. Blood routine: no blood transfusion or blood products usage within 14 days, G-CSF or other hematopoietic stimulator was not used. WBC counts $>$ 3000/ μ l, Absolute neutrophil count (ANC) \geq 1500 cells/ μ l, Platelet count \geq 100,000/ μ l, Hemoglobin \geq 9.0 g/dL.
8. AST, ALT and alkaline phosphatase \leq 2.5 times the upper limit of normal (ULN), Serum bilirubin \leq 1.5 x ULN, creatinine $<$ ULN
9. Prothrombin time (PT), international standard ratio (INR) \leq 1.5 \times ULN
10. Patients who have not received systemic chemotherapy or immunotherapy
11. Women of childbearing age must be willing to use adequate contraceptives during the study period of drug treatment;
12. Informed consent has been signed.

4.2 Exclusion Criteria:

1. Patients have received any prior systemic antitumor therapy;
2. Active bleeding within 3 months; Occurrence of arterial/venous thrombosis within 6 months; Hereditary or acquired bleeding (e.g., clotting dysfunction) or thrombotic tendencies; Full dose oral or injectable anticoagulants or thrombolytic drugs for therapeutic purposes are currently being used or have been used recently (10 days prior to the commencement of study treatment); Surgery (except for biopsy) was performed within 4 weeks prior to the study or the surgical incision was not fully healed; Aspirin ($>$ 325 mg/ day) or dipyridamole, ticlopidine, clopidogrel, and silitazone are currently being used or have recently been used (10 days prior to the study).
3. Systemic corticosteroids or other systemic immunosuppressive drugs were used within 2 weeks prior to treatment. Immunosuppressive drugs were started or expected to be used during the trial. Inhaled corticosteroids, physiologic replacement doses of glucocorticoids are allowed.
4. Certain or suspected distant metastases.
5. The patient has a history of autoimmune disease.
6. Serious uncontrolled systemic diseases, such as severe active infections;
7. A person is known to be infected with the immunodeficiency virus (HIV) or known to be HIV-positive;
8. Patients have suffered from other malignancies in the past 5 years except cervical carcinoma in situ or basal cell carcinoma of the skin
9. Untreated chronic hepatitis B or chronic hepatitis B virus (HBV) carriers (HBV DNA $>$ 500

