IU/mL) or active HCV carriers with HCV RNA can be detected. Remarks: Inactive hepatitis B surface antigen (HBsAg) carriers, treated and stable hepatitis B patients (HBV DNA < 500 IU/mL) may be enrolled

10. Anti-infective therapy was not discontinued 14 days before the study;
11. A prior history of interstitial lung disease, drug-induced interstitial lung disease, radiation pneumonia, and symptomatic interstitial lung disease or the presence of active pneumonia on a chest CT scan within 4 weeks prior to the study.
12. Patients have a history of intestinal obstruction within six months. Patients with incomplete obstruction syndrome of ileus at the time of initial diagnosis may be enrolled in the study if they have received definitive (surgical) treatment to resolve the symptoms, as assessed by the investigator.
13. Patients have non-resectable factors, including surgical contraindications
14. Patients Have high blood pressure that cannot be well controlled by antihypertensive medication (systolic \geq 140 mmHg or diastolic \geq 90 mmHg)
15. Urine routine indicated urinary protein \geq ++ and confirmed 24-hour urinary protein >1.0g;
16. Known to be allergic to any study drug;
17. Patients have participated in other drug clinical studies within 4 weeks before enrollment;
18. Lactating women
19. According to the judgment of the researcher, the patient may have other factors that may affect the results of the study or cause the study to be terminated, such as alcohol abuse, drug abuse, other serious diseases (including mental diseases) requiring combined treatment. Patients have severe laboratory abnormalities, which will affect the safety of the patient.

5 Clinical Assessments

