5.3 Primary Study Endpoint

Tumor regression rate of MSS/pMMR patients (Pathological response, percentage of TRG2-4 to all MSS patients, Dworak criteria)

TRG Dworak criteria: Grade 0: no regression; Grade 1: dominant tumor mass with obvious

fibrosis and/or vasculopathy; Grade 2: dominantly fibrotic changes with few tumor cells or groups (easy to find); Grade 3: very few (difficult to find microscopically) tumor cells in fibrotic tissue with or without mucous substance; Grade 4: no tumor cells, only fibrotic mass (total regression or response).

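### The main analysis set makes eligibility and undefined treatment conditions of the primary denominator, is not reconciled with an endpoint based on all MSS patients, and lets treated patients be dropped after outcome is known

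*Protocol*

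**What the plan says.** Protocol section 10.1 defines the FAS as "Patients who met the enrollment criteria and were treated with the study protocol" and gives it priority: "The efficacy evaluation of this study will be based on FAS and PPS, in which FAS is the main analysis set". Membership thus has two conditions, eligibility and treatment under the protocol. Neither comes with a minimum exposure, a cut-off date or a named decision-maker.

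The primary endpoint in section 2.1, repeated in 5.3, is the "percentage of TRG2-4 to all MSS patients, Dworak criteria". It contains no eligibility or treatment condition.

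Other relevant text:

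- The safety set in 10.1 requires enrolment, at least one cycle and one safety record, but not eligibility.
- Section 9 lists failure of the entry criteria as a protocol violation and allows no waivers. It leaves withdrawal for a violation to the sponsor in consultation with the investigator.
- Section 5.2 places pathological assessment after the operation.
- Section 10.2 fixes the SAP before database lock.
- The SAP defines no analysis set and names no denominator. Its primary analysis is a rate with a 95% CI.
- Neither document says how a treated patient without surgery or without a TRG is counted.

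**The concern.** In a single-arm trial the response rate is the whole result, and no control arm offsets a bias in its denominator. Two routes lead out of the FAS after TRG is known.

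1. **Late re-judgment of baseline eligibility.** Some entry criteria need judgment. Examples in section 4.2 are "Certain or suspected distant metastases" and "Patients have non-resectable factors, including surgical contraindications". A baseline scan can be re-read, and nothing says this must happen before TRG is available or without knowledge of it.
2. **The undefined treatment condition.** A patient who stops early or has no operation could be held not to have been treated under the protocol.

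If those who leave are mostly non-responders, the rate is biased upward and the chance of a false positive result grows. Fixing the SAP before lock does not help, because it does not cover eligibility rulings on individual patients.

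**Working it through.** **Inputs.** From Protocol 3.2 and SAP section 1: Simon optimal two-stage design, one-sided alpha 0.05, power 0.80, p0 = 0.225, p1 = 0.40, 10% dropout, 64 enrolled. The number removed, k, is not in the documents; it is assumed, over 0 to 7. The calculation also assumes that all 64 patients are MSS/pMMR, which the documents do not state.

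**Step 1: reproduce the plan's figure.** The documents give no stage sizes or boundaries. Exact search for the optimal design gives: continue if more than 5 of 19 respond, succeed if more than 17 of 57 respond. The probability of success is

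P(success | p) = Σ over x = 6 to 19 of P(X1 = x) × P(X2 > 17 − x), with X1 ~ Bin(19, p) and X2 ~ Bin(38, p).

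This is 0.0499 at p = 0.225 and 0.804 at p = 0.40. Then 57 / 0.90 = 63.3, rounded up to 64. The stated sample size is reproduced, and this point does not question it.

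**Step 2: worst-case removal under that boundary.** Suppose 57 + k patients are treated, k stage-2 non-responders are removed, and the remaining 57 are judged against the unchanged boundary. Success still needs at least 18 responders, now drawn from 57 + k patients. In the formula, X2 becomes Bin(38 + k, p).

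**Step 3: the same removal under a confidence-interval criterion.** The planned analysis is a rate with a 95% CI, so success might instead mean a lower bound above 22.5%. Assuming Clopper-Pearson limits, 19/57 has a lower bound of 21.4% and 20/57 has 22.9%, so 20 responders are needed in 57. Replace 17 by 19 in the formula and keep the first-stage rule.

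| k removed | Treated | Type I error, >17/57 | Type I error, CI criterion |
|---|---|---|---|
| 0 | 57 | 5.0% | 1.6% |
| 3 | 60 | 6.9% | 2.7% |
| 6 | 63 | 9.0% | 4.0% |
| 7 | 64 | 9.7% | 4.5% |

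Without the first-stage rule, the CI criterion gives 2.1%, 3.6% and 5.8% for k = 0, 3 and 6.

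**Step 4: effect on the estimate.** With 18 responders, 18/57 = 31.6%, against 18/60 = 30.0% (k = 3) and 18/63 = 28.6% (k = 6). The shifts are 1.6 and 3.0 percentage points. For 20 responders, 20/57 = 35.1% (95% CI 22.9 to 48.9), while 20/64 = 31.3% (20.2 to 44.1). Here the lower bound clears 22.5% only because seven non-responders are absent.

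**Step 5: how extreme the worst case is.** If removal were unrelated to outcome and p = 0.225, the chance that all removed patients are non-responders is 0.775^k: 0.775³ = 47% for k = 3 and 0.775⁶ = 22% for k = 6.

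**The case against.** The strongest reply has four parts.

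**Entry criteria are not on-treatment events.** A reader might infer that patients who progress or become unresectable would fail the enrolment criteria and leave the FAS. The documents do not support this. Section 5.2 treats new distant metastasis as progression, inclusion criterion 4 asks only that surgery is planned, and section 8 says that stopping treatment does not automatically withdraw a patient. A reader might also take exclusion 3, "Immunosuppressive drugs were started or expected to be used during the trial", to make anyone given steroids for an immune-related event ineligible. That reading is strained: the item is worded as a screening exclusion, and section 6.2.2.2 itself relies on corticosteroids to manage such events. Neither inference is part of this point. What remains is late re-judgment of baseline findings, and the undefined treatment condition.

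**The two denominators may be compatible.** The phrase about all MSS patients may only name the cohort, since MSI-H/dMMR patients have their own endpoints. That is a fair reading, but neither document states it, so the denominators are unreconciled rather than plainly contradictory.

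**Removals should be few and visible.** Waivers are not allowed, and section 10.2.1 requires enrolment, withdrawals and major violations to be described. This limits the likely size and helps a reader detect removals. It does not set when, or with what knowledge of TRG, rulings are made.

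**The error rates depend on an unstated rule.** This stands. The >17/57 boundary is reconstructed, and under the CI criterion with the first-stage rule, type I error stays below 5% up to seven removals.

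**Conclusion.** The point holds as a weakness in a stated analysis rule. The main efficacy set depends on eligibility and on an undefined treatment condition, the endpoint text has neither, and nothing separates membership rulings from knowledge of TRG.

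The plausible size is modest. For 3 to 6 removals at 18 responders, the estimate moves by 1.6 to 3.0 percentage points. Type I error rises to 6.9% to 9.0% from 5.0% under the reconstructed Simon boundary, or to 2.7% to 4.0% from 1.6% under the CI criterion with the same first stage. These are worst cases: they assume that every removed patient is a stage-2 non-responder, that the boundary is unchanged, and that the number removed is as shown.

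A reader might conclude that the rule is designed to discard failures, or that it will do so. The documents do not show that. The rule could equally remove responders.

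**What to change.** In Protocol 10.1 and in the SAP:

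- Define the primary efficacy set as every enrolled MSS/pMMR patient who received at least one dose of any study drug, whatever is later found about eligibility and whether or not surgery took place.
- Count a patient in this set without a TRG as a non-responder. This is a missing-outcome rule, but the denominator is not settled without it.
- Move the eligibility condition to the per-protocol set or a sensitivity set. Base its exclusions on pre-treatment data only, and decide them before TRG is known.
- State the success boundary for the number actually analysed. Applying >17 responders to 64 patients would itself give the 9.7% shown above.

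The cost is a few sentences in each document, with no added data collection and no change to the planned 64. The reported response rate may be slightly lower, because treated patients without a TRG count as failures.

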10.2 Statistic Method

The statistical analysis plan is determined before the database is locked, and the statistical analysis is carried out in strict accordance with the statistical analysis plan.

All statistical analysis will be calculated using SAS9.4 or above version of statistical analysis

software. All confidence intervals (CI) are applied with 95% confidence. For measurement data, mean \pm standard deviation or median (minimum value, maximum value) will be used for statistical description; Frequency (rate) was used for statistical description of counting data. The Kaplan-Meier method was used to calculate the median value and 95%CI for time event data, and the survival curve was plotted.

10.2.1. Subject Distribution

Descriptive analysis of subject distribution, including but not limited to enrollment, withdrawal, and major protocol violations. The reasons for screening failure and the reasons for quitting the test were summarized.

